# SCHEMATIC OF STUDY ENROLLMENT

# SCHEMATIC OF GENETIC SCREENING PHASE

# SCHEDULE OF STUDY VISITS AND PROCEDURES: VISION COHORT 1 & VISION COHORT 2

Visit	Screening	Baseline	12M	24M	36M	48M
Visit Target Windows	(Up to Day	(Day 0) b	Wk	Wk	Wk	Wk
	-60) a		$52 \pm 4^{\circ}$	$104 \pm 4^{c}$	156± 4°	208± 4°
Participant-Level Procedures						
Informed Consent / Eligibility Assessment	Х					
Demographics/Screening Medical History (including pre-existing conditions,	X					
symptomology history, patient-reported daily activities, and medications)	Λ					
Determination of Vision Cohort	X					
3mm punch skin biopsy i		Х				
Concomitant Medications	Х	Х	Х	Х	Х	Х
Adverse Events		Х	Х	Х	Х	Х
Patient Reported Outcomes (PROMIS-29, MRDQ, ViSIO-PRO, LVP-FVQ II) h		Х		Х		Х
Ocular Procedures - All testing performed in each eye						
Complete Ophthalmic Exam f	Х		Х	Х	Х	Х
Intraocular Pressure g	Х		Х	Х	X	Х
Visual acuity (including refraction, ETDRS, BRVT if needed, LLVA if needed)	Х		Х	Х	X	Х
SD-OCT volume scans (Heidelberg Spectralis)		Х	Х	Х	Х	Х
SD-OCT vertical and horizontal scans (Heidelberg Spectralis)		Х	Х	Х	Х	Х
Axial Length and Corneal Curvature measurements		Х		Х		Х
Fundus Autofluorescence (FAF) (Optos)		Х	Х	Х	Х	Х
Ultra-Widefield Color Photo (Optos)		Х	Х	Х	Х	Х
Optical coherence tomography angiography (OCTA) j		Х	Х	Х	Х	Х
Red reflex photo k		Х	Х	Х	Х	Х
Full-field Stimulus Threshold (Diagnosys Espion)		Х	Х	Х	Х	Х
Static perimetry (Octopus 900 Pro)		X d	Х	Х	Х	Х
Fundus guided microperimetry (MAIA)		X d	Х	Х	Х	Х
Kinetic VF III4e for Vision Cohort definition only	Xe					

**a.** All Screening Visit testing must be completed on the same day (except for kinetic VF, as noted below).

b. Baseline Visit date (defined as the start date of all Baseline testing) must be no later than two (2) weeks after receiving confirmation of meeting *final study cohort criteria* from the CGA. All Baseline testing must be completed within ten (10) days of the Baseline Visit date, except PROs as specified.

c. All Follow up visit testing must be completed on the same day, except PROs as specified.

**d.** For static perimetry and microperimetry, all Vision Cohort 1 and 2 participants will complete two (2) tests at baseline. The results will be compared according to the *visual field criteria* to determine if a third test is needed.

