558 559 560 561 562 563	detailed in and certif	wing procedures will be performed at the Baseline Visit. The testing procedures are in the GYROS Clinical Site Manual of Procedures . An overview of the equipment fication requirements for all testing is in Chapter 5.1: Study Procedure nents . All ocular testing will be performed in each eye, OD first and then OS. Baseline es will last approximately seven $(7) - eight (8)$ hours. Baseline procedures will span 10) days.
564	3.3.1	Baseline Data Collection and Testing Cohorts 1 & 2
565	1.	Medical updates to include:
566		• New or changed adverse events (AEs)
567		New ocular procedures
568		New or changed medications
569		• Request medical records and laboratory records if applicable.
570	2.	Patient Reported Outcomes
571		
 
Adults: PROMIS®-29, MRDQ, ViSIO-PRO
 

572		
 
Adolescents: LPV-FVQ II, ViSIO-PRO
 

573		Children: LPV-FVQ II
574 575 576		• The PROs may be completed in person or remotely (phone or other remote methods) any time within six (6) months of the Baseline Visit (not required to be the same day as the rest of the Baseline Visit).
577	3.	Skin biopsy (3mm punch skin biopsy)
578		• Ship to Johns Hopkins University Department of Genetic Medicine Research Lab
579	4.	Spectral Domain Optical Coherence Tomography (SD-OCT)
580		Volume Scan
581		Vertical and Horizontal Scan
582	5.	Axial Length and Corneal Curvature Measurements
583	6.	Fundus Autofluorescence
584	7.	Widefield color photo

585	8. Optical coherence tomography angiography (OCTA)
586	• Ancillary test; may be waived with approval from the Coordinating Center
587	9. Red reflex photo
588	10. Full field Stimulus Threshold (FST)
589	11. Static perimetry
590 591	• Two (2) tests will be performed. The clinical site will compare the certified technician determined mean sensitivity from test one (1) versus test two (2).
592 593 594 595	
 
(a) If the absolute value of the difference between the two tests is ≤ 2.4 dB, then the participant passes static perimetry reliability criteria. A third test is not needed.
 

596 597 598	(b) If the absolute value of the difference between the two tests is > 2.4 dB, then the participant does not pass static perimetry reliability criteria. A third test will be required .
599	12. Fundus guided microperimetry

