701 702	
 
The Clinical Site Coordinator will transcribe the data from the food record on the FFB Study Website.
 

703 704 705	
 
A Central Dietitian Reviewer (CDR) will review food record on FFB Study Website to determine nutritional content. This information will be entered into the FFB Study Website.
 

706	(3) Sample Collection
707 708 709 710	
 
At the annual Follow-up Visits, the Clinical Site Personnel will collect one         
 
(1) fasting plasma sample on all participants and ship to KKI. The sample collection procedures are detailed in the GYROS Clinical Site Manual of Procedures.
 
 
 

711 712 713 714	At the annual Follow-up Visits, the Clinical Site Personnel will collect one (1) fasting blood spot fingerstick on all participants and ship to KKI. The sample collection procedures are detailed in the GYROS Clinical Site Manual of Procedures.
715 716 717	
 
At the annual Follow-up Visits, the Clinical Site Coordinator would request the most recent lab records with an albumin result if the participant indicated they are currently on an arginine-restricted diet.
 

 
718
 
719
 
720
 
721
 
722
 
723
 
	
 
Every four (4) months between annual Follow-up Visits, one (1) fasting blood spot fingerstick will be collected on all participants. The participant or caretaker will collect the sample and ship to the central laboratory, KKI. The blood spot collection kits and instructions will be provided. The sample collection procedures are detailed in the GYROS Clinical Site Manual of Procedures.
 

724	4.4 Follow-up Procedures
725 726 727 728 729	The following procedures will be performed at the Follow-Up Visits, unless otherwise specified. The testing procedures are detailed in the GYROS Clinical Site Manual of Procedures. An overview of the equipment and certification requirements for all testing is in Chapter 5.1: Study Procedure Requirements . All ocular testing will be performed in each eye, OD first and then OS. Follow-up visit procedures will last approximately seven (7) – eight (8) hours.
730	4.4.1 Follow-up Data Collection and Testing Cohorts 1 & 2
731	1. Medical updates to include:
732	• New or changed adverse events (AEs)
733	
 
New ocular procedures
 

734	
 
New or changed medications
 

735	• Request medical records and laboratory records if applicable.

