### 1150 8.3.1 Primary Objective Analysis

1151 The primary objectives of the natural history study and brief analysis plan for each are as 1152 follows.

**1.** Natural History 1153 (a) Characterize the natural history of retinal degeneration associated with 1154 disease-causing OAT variants over four (4) years, as measured using 1155 functional, structural, and patient-reported outcome measures. 1156 1157 i. Functional and structural measures: The distribution of each 1158 outcome at each visit will be summarized (including tabulating 1159 categorically, as well as means, SDs, medians, quartiles, ranges; both 1160 the absolute change and percent change will be evaluated, tests 1161 performed multiple times per visit will be analyzed using the average 1162 of all available tests). To determine the average annual rate of 1163 progression in the population for each outcome, a mixed effects model 1164 will be fit using all available outcome data at baseline and all annual 1165 visits. Both the correlation in outcomes over time and the correlation 1166 in outcomes between eyes will be accommodated by the model. 1167 Mixed models adequately accommodate missing values when missing 1168 values are missing at random (MAR). A second method of 1169 accommodating missing values will be through multiple imputation for 1170 the outcome values for all missing time points (including participants 1171 who discontinue follow up prior to forty-eight (48) months). 1172 Secondary analyses using binary definitions of outcome measures will 1173 also be explored in time to event analyses; Kaplan-Meier estimates 1174 with 95% confidence intervals will be calculated. 1175 1176 **PRO measures:** The scoring of each questionnaire will be completed ii. 1177 according to the procedures recommended by the developers of the 1178 questionnaire for each instrument. Baseline scores will be cross 1179 tabulated with categorical (severity of disease) versions of the outcome 1180 measures of interest at baseline. Changes in scores will be cross 1181 tabulated with binary (progression of disease) versions of the outcome 1182 measures of interest at the 24- and 48-month visits. A generalized 1183 linear model adjusted for baseline differences will be explored. 1184

1185	Partially completed questionnaires will be managed using methods
1186	recommended by the developers of the specific questionnaire. When
1187	no questionnaire is completed, we will use statistical methods that

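### For perimetry and microperimetry, the averaged Baseline and single-test follow-ups differ in test conditions, and the fitted slope cannot separate that difference from change over time, in either direction

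*Protocol*

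**What the plan says.** **Baseline.** Footnote d of the visit schedule for Vision Cohorts 1 and 2 reads: "For static perimetry and microperimetry, all Vision Cohort 1 and 2 participants will complete two (2) tests at baseline". The two results are compared "to determine if a third test is needed". Section 3.3.1 item 11 gives the static perimetry rule: if the "difference between the two tests is ≤ 2.4 dB, then the participant passes static perimetry reliability criteria", and otherwise a third test is done. Item 12 has a similar rule for microperimetry. Neither test is done at Screening, so Baseline test 1 is the first in the study. Footnote b allows Baseline testing to spread over ten "days of the Baseline Visit date, except PROs as specified".

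**Follow-up.** Section 4.4.1 items 13 and 14 list each test once, with no repeat rule. Footnote c says: "All Follow up visit testing must be completed on the same day, except PROs as specified".

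**Analysis.** Section 8.3.1 item 1(a)i states that tests "performed multiple times per visit will be analyzed using the average" of all those available. It then estimates the average annual rate of progression with a mixed effects model on Baseline and all annual visits. The model is said to handle correlation over time and between eyes. No term is named for test order or for the difference in conditions between Baseline and follow-up.

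**The concern.** Baseline differs from every later visit in three ways at once: it contains the first in-study test, it averages several tests, and it need not be completed in one day. All follow-ups share one set of conditions and Baseline alone has the other. Any systematic difference between the two is therefore a step after year 0, and a single straight-line slope absorbs part of it.

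The Impact section of the Protocol Summary says the study will establish progression rates, find the measures most sensitive to change, and supply variability for sizing a future trial. A step that affects perimetry and microperimetry, but not outcomes measured the same way at every visit, would distort both the perimetry rates and the comparison between measures.

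**Working it through.** **1. The protocol's own figures, for reference.** With 40 participants and an assumed inter-eye correlation of 0.8 (section 8.2.1), effective N = 40 × 2/(1 + 0.8) = 44.4. With an SD of 20%, the 95% half width is t(0.975, 43) × 20/√44 = 6.08%, against the stated 6%. Power for a 17% difference with 22 effective eyes per subgroup is 0.805 (normal) or 0.786 (noncentral t), against the stated figure of about 80%. These reproduce, and the present point does not affect them.

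**2. How a step enters the slope.** With visits at t = 0, 1, 2, 3, 4 the mean is 2 and Σ(t − 2)² = 10. The slope weights (t − 2)/10 are −0.2, −0.1, 0, 0.1, 0.2. A constant difference s at all four follow-ups contributes s × (−0.1 + 0 + 0.1 + 0.2) = 0.20s per year. A mixed model with random intercept and slope, complete data and equal residual variance gives the same weights. A simple Baseline-to-year-4 change carries the whole of s.

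**3. Practice.** Suppose test 1 alone reads L too low. A two-test Baseline is then low by L/2, so follow-ups sit L/2 higher and the slope moves by 0.20 × L/2 = +0.10L per year, which hides decline. With three tests the effect is 0.20 × L/3 = 0.067L.

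**4. Conditions on the follow-up day.** A loss F at every follow-up moves the slope by −0.20F per year, which adds apparent decline. With both effects, the net apparent decline is 0.20 × (F − L/2) per year, which is zero at L = 2F.

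**5. Sizes (all assumed).** The document gives no practice or day effect.

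| Assumed effect | Slope bias per year |
|---|---|
| L = 1 dB | hides 0.10 dB |
| L = 2.4 dB | hides 0.24 dB |
| L = 5% of Baseline | hides 0.5%, one tenth of the 5% annual decline assumed in section 8.2.4 |
| F = 2.5% of Baseline | adds 0.5%, one tenth of that decline |
| F = 5% of Baseline | adds 1.0%, one fifth of that decline |

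The 2.4 dB value is borrowed from the static perimetry pass limit only to mark the top of an illustrative range.

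**6. Averaging alone.** In simulation with a true slope of −5 and no step, the mean slope was −4.99, −5.00 and −5.01 for one, two and three Baseline tests. Only the spread changed: SD 3.16, 2.83 and 2.71 at an assumed residual SD of 10.

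**7. Precision of the alternatives** (residual part of the slope SE, in units of the residual SD, complete data):
- Single-test Baseline: √(0.04 + 0.01 + 0 + 0.01 + 0.04) = 0.316.
- Two-test averaged Baseline: √(0.04/2 + 0.06) = 0.283.
- First-test indicator with two Baseline tests: test 1 is absorbed, leaving 0.316. The ratio to the averaged analysis is 0.316/0.283 = 1.12.
- Months 12 to 48 only: Σ(t − 2.5)² = 5, so 1/√5 = 0.447. The ratio to a single-test Baseline is 0.447/0.316 = 1.41, and to the two-test averaged Baseline 0.447/0.283 = 1.58.

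Variation in true slopes between participants adds equally to each, so these ratios are upper limits.

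**The case against.** - **The stated test time is equal.** Section 3.3 gives Baseline about seven to eight hours, the same as section 4.4 gives a follow-up visit, and ten days is a limit, not a schedule. This stands. A reader might infer that follow-up is a longer test session, but the protocol does not say so. What remains is that follow-up must fit into one day and Baseline need not. The follow-up list also includes acuity, refraction, pressure and the ophthalmic examination, which were done at Screening and not at Baseline.
- **Participants may not be new to perimetry.** This stands. The protocol records no earlier testing either way, and section 1.5.1 describes most procedures as standard care. Test 1 is the first in the study, which is not the same as a first exposure.
- **Averaging is sound and destroys nothing.** This stands. The individual tests are still collected, and averaging affects precision, not the mean. The problem is a step between conditions, if one exists.
- **This is detail for a statistical analysis plan.** Section 8.1 calls the chapter a framework, and a fuller plan could add such analyses. But item 1(a)i is not silent: it fixes a specific rule for repeat tests and a specific set of visits for the slope.
- **Only two functional tests are affected.** This is correct, and it limits the weight of the point.

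**Conclusion.** The point holds in a limited form. For static perimetry and microperimetry in Vision Cohorts 1 and 2, a systematic Baseline/follow-up difference s cannot be separated from time under item 1(a)i. It biases the slope by 0.20s per year, assuming five equally spaced visits, complete data and equal residual variance.

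Three stronger readings are tempting, and the document supports none of them:
- **That the step will appear as progression.** Practice on the first test works the other way, and the net sign is unknown.
- **That the 2.4 dB limit measures the likely bias.** It is a pass rule for one participant's pair of tests. If the mean shift were that large, about half of the pairs would be expected to exceed it and need a third test.
- **That the multiplier is 0.25.** That requires a model giving the Baseline mean double weight, which the plan does not state.

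The true size cannot be set from the protocol. The change is worth making because it is cheap, the data are already collected, and the resulting rates are meant to guide a future trial. The primary FAF and ornithine outcomes are unaffected.

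**What to change.** Keep the averaged analysis in section 8.3.1 item 1(a)i. For static perimetry and microperimetry, add:

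1. The mean paired difference between Baseline test 2 and test 1, with a confidence interval that allows for two eyes per participant. This shows directly whether there is a practice shift.
2. A sensitivity model with each test as its own record and an indicator for the first in-study test. Where only two Baseline tests were done, this is equivalent to a Baseline without test 1.
3. A sensitivity slope from months 12 to 48 only, where all visits share the same schedule. This is needed because the first-test indicator leaves a follow-up-day step in the slope at 0.20s per year.

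The cost is analysis wording and some precision. The residual part of the slope SE is about 12% larger for (2) than for the averaged two-test analysis. For (3) it is up to about 41% larger than with a single-test Baseline (up to about 58% against the averaged two-test one). Both should therefore remain sensitivity analyses. No visit, test or sample-size figure changes.

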## 500 **2.4.1.2 Genetics Committee Review**

A Genetics Committee will review the genetic documentation of participants with verified **final study cohort criteria** and **enrolled into the study cohort** for interpretation and evaluation of whether the *OAT* mutations are causative of the disease (i.e., pathogenic, likely pathogenic). Cases that are not confirmed as disease causing will remain in the study and will not be considered ineligible. However, their data may be analyzed separately from those with

506 pathogenic mutations.

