### 976 **7.2 Prohibited Medications, Treatments, and Procedures**

### 977 **7.2.1 Prohibited Medications and Treatment for** *OAT***-Related Retinal Degeneration**

Participants who are **enrolled into the final study cohort** should not receive IRD treatments during the study. This includes enrolling into an experimental treatment trial of underlying conditions related to *OAT* mutations during the 4-year study duration. However, if the participants enroll in a treatment trial the Executive Committee will be consulted and will

- determine if the participant may continue in the study.
- 983 Examples of prohibited medications and treatments include, but are not limited to the following:
- use of ocular stem cell or gene therapy 984 ocriplasmin 985 ٠ ophthalmic oligonucleotide 986 ٠ Ozurdex (dexamethasone) 987 • Iluvien or 988 Yutiq (fluocinolone acetonide) intravitreal implant 989 ٠ Amiodarone, chloroquine, deferoxamine, hydroxychloroquine, pentosan polysulfate, 990 ٠ tamoxifen, thioridazine 991

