### 1010 7.5 Participant Withdrawal

- 1011 Participation in the study is voluntary, and a participant may withdraw at any time. For
- 1012 participants who withdraw, their data will be used up until the time of withdrawal.

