### 1022 **8.2 Sample Size**

The sample size evaluation focuses on objective 1a of the study, to characterize the natural 1023 1024 history of retinal degeneration associated with disease-causing OAT variants in the presence of standard care dietary treatment regimens over four (4) years, using functional, structural, and 1025 1026 patient-reported outcome measures. A justification of the selected sample size using percent 1027 change for the outcomes of interest is outlined. The precision of estimates and of the correlation between structure-based, function-based, and metabolic-based outcomes involved in objective 1028 two (2) and of the correlation between eyes in the outcomes is also provided. Calculations to 1029 1030 address objective three (3), explore risk factors associated with progression (i.e., compare

1031 subgroups for dichotomous risk factors), are summarized.

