1188	mitigate the impact of missing data, specifically, mixed effects
1189	regression models and multiple imputation for the outcome values for
1190	all missing time points.
1191	
1192	(b) Characterize the natural history of ornithine levels associated with disease-
1193	causing OAT variants in the presence of standard care dietary treatment
1194	regimens over four (4) years.
1195	
1196	i. Longitudinal annual measures of ornithine will be explored by
1197	graphing the values for everyone ("spaghetti" plots) and analyzed to
1198	detect any linear trend in time with mixed effects models.
1190	detect any mical field in time with mixed effects models.
1200	(c) Determine within-patient variability of ornithine levels associated with
1200	disease-causing OAT variants in the presence of standard care dietary
1201	treatment regimens over four (4) years.
1202	
1203	i. The within-person standard deviation of ornithine levels will be
1204	estimated for the group of patients using a mixed effects model.
1205	Models will be based on levels from blood dot tests and from plasma
1206	testing over the four (4) years to determined long -term variability and
1207	on levels from blood dot tests over periods of six (6) months and of
1208	twelve (12) months to determine short-term variability. The coefficient
1209	of repeatability will be calculated to estimate the difference from
1210	baseline that would need to be exceeded to indicate that a treatment
1211	was causing an effect beyond random variability.
1212	2. Metabolic, Structure, and Function Relationships
1213	(a) Evaluate cross-sectional associations at baseline and each annual visit with
1214	scatterplots and Spearman correlation coefficients. Evaluate the association of
1215	changes in each outcome measure with changes the other outcome measures
1216	at each visit with scatter plots and Spearman correlation coefficients. Use
1217	mixed effects regression models to evaluate the association of change in each
1218	outcome measure with changes in each of the other outcome measures. With
1219	so many outcomes and only forty (40) patients, results will be interpreted
1220	cautiously because of both low powers to detect clinically meaningful
1221	associations and elevated Type I error rates due to multiple comparisons.
1222	3. Identify Rapid Progressors
1223	(a) The distribution of each outcome in terms of both absolute change and percent
1224	change from baseline to four (4) years will be summarized (including

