1225	tabulating categorically, as well as means, standard deviations, medians,
1226	quartiles), stratified by categorical levels of each potential risk factor of
1227	interest (listed below). Potential risk factors to evaluate include phenotypic
1228	factors including the baseline level of each of the structural and functional
	-

1229	measures and ornithine level, genotype, and adherence to the arginine-
1230	restricted diet as noted below. Univariable regression models of each outcome
1231	measure will be fit for each of the potential risk factors. With so many
1232	potential risk factors and outcomes and only forty (40) patients, results will be
1233	interpreted cautiously because of both low powers to detect clinically
1234	meaningful differences and elevated Type I error rates due to multiple
1235	comparisons.
1236	
1237	i. Phenotypic:
1238	
 
Age of onset of initial vision symptoms
 

1239	
 
Gender
 

1240	Race/ethnicity
1241	
 
Body weight/BMI
 

1242	
 
Lens Status (phakic/pseudophakic/aphakic) and area of
 

1243	subcapsular cataract on red reflex photos
1244	
 
Baseline foveal avascular zone (FAZ) area and macular vessel
 

1245	density on OCTA
1246	
 
Baseline visual acuity
 

1247	
 
Baseline low luminance visual acuity
 

1248	
 
Baseline area of preserved retina on fundus autofluorescence
 

1249	and color photos
1250	
 
Baseline full Hill of Vision (HOV) on static perimetry
 

1251	
 
Baseline mean sensitivity on static perimetry
 

1252	
 
Baseline mean retinal sensitivity on microperimetry
 

1253	
 
Baseline full-field stimulus (FST) levels
 

1254	
 
Baseline ERG amplitude and timing
 

1255	
 
Baseline ellipsoid zone (EZ) area on OCT
 

1256	
 
Baseline ornithine level
 

1257	
1258	ii. Genotypic
1259	
 
Characterizations of the OAT variants
 

1260	
1261	iii. Environmental Factors
1262	
 
Adherence to arginine-restricted diet
 

1263	
 
Smoking
 

1264	

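### Should the protocol say how visits after entry into a treatment trial are handled in the natural-history analyses?

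*Protocol*

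**What the plan says.** Section 7.2.1 of the protocol says that enrolled participants should not receive treatments for inherited retinal disease or join an experimental trial during the four years. It then provides for the exception: if "participants enroll in a treatment trial the Executive Committee will be consulted and will" "determine if the participant may continue in the study". It does not mention the data collected afterwards.

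Section 8.3.1, item 1(a)i, obtains the average annual rate of progression from a mixed effects model that "will be fit using all available outcome data at baseline and all annual" visits. Item 1(c) estimates within-person variability of ornithine: "Models will be based on levels from blood dot tests and from plasma" testing over the four years, with shorter windows as well. Item 3 fits "Univariable regression models of each outcome" measure on each risk factor. None of these items has a rule for visits after trial entry.

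Two nearby rules do not reach the case. Section 7.5 covers withdrawal: for "participants who withdraw, their data will be used up until the time of withdrawal". Section 2.4.1.2 covers variants not confirmed as disease causing, whose carriers stay in the study although "their data may be analyzed separately from those with" pathogenic mutations.

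The target is stated in section 8.2 and in the Protocol Summary as natural history in the presence of "standard care dietary treatment regimens over four (4) years, using functional, structural, and" patient-reported measures.

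**The concern.** Taken together, the sections seem to leave a gap. A retained trial entrant has not withdrawn, so section 7.5 does not stop the data. Section 2.4.1.2 does not apply. Item 1(a)i asks for all available data. On a literal reading, visits under an experimental therapy would enter an estimate that is meant to describe the disease under standard-care diet.

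This would matter because the results are meant to plan a later treatment trial. An effective therapy would pull the estimated rate towards stability, always in the same direction, and the confidence interval would not show it. If the therapy also lowered ornithine, the within-person SD would rise. So would the coefficient of repeatability, which item 1(c) uses as the change a future treatment must exceed. The protocol does provide for separate analysis of one other retained group, which makes the silence here more noticeable.

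**Working it through.** **Is there a rule?** None of the sections on trial entry, prohibited treatment, surgery, withdrawal, separate analysis or data analysis (2.3.1.3, 2.4.1.2, 7.2.1, 7.2.2, 7.5, 8.3.1) sets apart visits made after trial treatment starts. The silence is real. What remains is how large its effect could be.

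**Inputs from the protocol.** 40 participants, equal to 44 effective eyes at an inter-eye correlation of 0.8 (sections 8.2.1 and 8.2.4); SD of the four-year percent change 20% and decline 5% per year (both assumptions in 8.2.4); annual visits at years 0 to 4; 13 blood spots per person, at months 0, 4, ..., 48 (sample collection schedule).

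**Assumptions not in the protocol.** The number of entrants n, the year of entry k and the treatment effect. Ranges are shown.

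**Planned precision.** 1.96 × 20/√44 = 5.9%, or 6.1% with the t quantile on 43 df. This reproduces the stated 6%. Per year, the standard error is 20/√44/4 = 0.754 points and the half width is 6.08/4 = 1.52 points.

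**Slope of one entrant.** Untreated, y = −5t. The least-squares slope over years 0 to 4, with the effect starting after year k, is:

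| Effect | k = 1 | k = 2 | k = 3 |
|---|---|---|---|
| Decline halved | −3.00 | −3.75 | −4.50 |
| Decline stopped | −1.00 | −2.50 | −4.00 |

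**Shift of the mean slope** = (n/40) × (entrant slope + 5), in points per year:

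| Entrants and effect | k = 1 | k = 2 | k = 3 |
|---|---|---|---|
| 1, halved | 0.050 | 0.031 | 0.013 |
| 1, stopped | 0.100 | 0.063 | 0.025 |
| 4, halved | 0.200 | 0.125 | 0.050 |
| 4, stopped | 0.400 | 0.250 | 0.100 |

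**Coverage of the nominal 95% interval** (noncentral t, 43 df, noncentrality = shift/0.754): 94.95% at a shift of 0.05, 94.8% at 0.10, 94.2% at 0.20 and 91.9% at 0.40. The largest shift in the table is 0.40/1.52 = 26% of the half width.

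**Ornithine variability, item 1(c).** Take a random-intercept model without a time slope, and a step of d within-person SDs after month 24, so that 6 of the 13 samples are affected. Each entrant adds variance d² × (6/13)(7/13)(13/12) = 0.269d². The SD ratio is √(1 + (n/40) × 0.269d²):

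| Entrants | d = 1 | d = 2 | d = 3 |
|---|---|---|---|
| 1 | 1.003 | 1.013 | 1.030 |
| 4 | 1.013 | 1.052 | 1.115 |

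The coefficient of repeatability rises by the same ratio. These rows apply only if the treatment changes ornithine, and only to the four-year blood-spot model. In the 6- and 12-month windows, only a window that spans the step is affected.

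**The case for a change.** The best argument for a change is that this is more than silence. Section 7.2.1 foresees retained entrants, item 1(a)i names the data to be used, and an analysis plan that dropped those visits would have to depart from that wording. Entry is also conceivable: the exclusion in 2.3.1.3 concerns only trial entry expected at screening, follow-up lasts four years, and the study is meant to prepare the ground for treatment trials and identify candidates for them. A rule fixed in advance would avoid a later choice about whose visits count.

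Part of this stands. No section covers the case, and settling it before any entrant appears is good practice. The rest is weaker. Section 8.2.1 contrasts a sample size based on change from baseline to year 4 with analyses that use every annual visit, and the sentences after the model statement in 8.3.1 deal with correlation over time and missing values. In that setting, the phrase about available data means every time point and incomplete follow-up. It does not decide what to do with treated visits. Section 8.1 calls the chapter a synopsis and a framework, and 8.3.1 calls its content brief, so handling treatment received during follow-up is ordinary work for the statistical analysis plan. The parallel with 2.4.1.2 is loose as well, because that section only permits separate analysis and fixes nothing.

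A broad remedy has costs of its own. Cutting all data at the first treatment listed in 7.2.1 would catch agents such as tamoxifen or amiodarone, which are not trial therapies, and would remove every later visit of that person from a cohort of about 40 to 45. Cutting at trial entry whatever the arm would also discard control-arm visits that may be valid natural history. Both would lean on the missing-at-random assumption, although entering a trial may depend on progression.

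**Conclusion.** No change to the protocol is needed. The gap is one that analysts would fill sensibly: the target is natural history under standard-care diet, so visits under an experimental therapy fall outside it, and the statistical analysis plan is the place to say so. The event has to get past an exclusion at screening, a prohibition during follow-up and a Committee decision before it can affect any estimate.

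Its size rests wholly on assumed entrants and effects. One entrant with decline halved moves the rate by 0.01 to 0.05 points per year against a half width of 1.52, and coverage stays at about 95%. Coverage of 91.9% needs four of 40 participants to enter after year 1, all to be retained and all to stop declining. The increase in ornithine variability is 3.0% or less with one entrant and reaches 11.5% only with four entrants and a step of three within-person SDs. It arises only if the therapy alters ornithine.

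The judgement would differ if several participants entered trials early and were kept. Their visits could then be flagged and the rate reported with and without them, with control-arm visits left to the statistician's judgement. Nothing in the present text prevents that.
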